Appendix 2.3 Blood Pressure Levels for Boys by Age and Height Percentile

Blood Pressure Levels for Boys by Age and Height Percentile

Age (Year)	BP Percentile ↓	Systolic BP (mmHg)								Diastolic BP (mmHg)							
		← Percentile of Height →								← Percentile of Height →							
		5th	10th	25th	50th	75th	90th	95th	99th	5th	10th	25th	50th	75th	90th	95th	99th
1	50th	80	81	83	85	87	88	89	34	35	36	37	38	39	39	39	
	90th	94	95	97	99	100	102	103	49	50	51	52	53	53	54	54	
	95th	98	99	101	103	104	106	106	54	54	55	56	57	58	58	58	
	99th	105	106	108	110	112	113	114	61	62	63	64	65	66	66	66	
2	50th	84	85	87	88	90	92	92	39	40	41	42	43	44	44	44	
	90th	97	99	100	102	104	105	106	54	55	56	57	58	58	59	59	
	95th	101	102	104	106	108	109	110	59	59	60	61	62	63	63	63	
	99th	109	110	111	113	115	117	117	66	67	68	69	70	71	71	71	
3	50th	86	87	89	91	93	94	95	44	44	45	46	47	48	48	48	
	90th	100	101	103	105	107	108	109	59	59	60	61	62	63	63	63	
	95th	104	105	107	109	110	112	113	63	63	64	65	66	67	67	67	
	99th	111	112	114	116	118	119	120	71	71	72	73	74	75	75	75	
4	50th	88	89	91	93	95	96	97	47	48	49	50	51	51	52	52	
	90th	102	103	105	107	109	110	111	62	63	64	65	66	66	67	67	
	95th	106	107	109	111	112	114	115	66	67	68	69	70	71	71	71	
	99th	113	114	116	118	120	121	122	74	75	76	77	78	78	79	79	
5	50th	90	91	93	95	96	98	98	50	51	52	53	54	55	55	55	
	90th	104	105	106	108	110	111	112	65	66	67	68	69	69	70	70	
	95th	108	109	110	112	114	115	116	69	70	71	72	73	74	74	74	
	99th	115	116	118	120	121	123	123	77	78	79	80	81	81	82	82	
6	50th	91	92	94	96	98	99	100	53	53	54	55	56	57	57	57	
	90th	105	106	108	110	111	113	113	68	68	69	70	71	72	72	72	
	95th	109	110	112	114	115	117	117	72	72	73	74	75	76	76	76	
	99th	116	117	119	121	123	124	125	80	80	81	82	83	84	84	84	
7	50th	92	94	95	97	99	100	101	55	55	56	57	58	59	59	59	
	90th	106	107	109	111	113	114	115	70	70	71	72	73	74	74	74	
	95th	110	111	113	115	117	118	119	74	74	75	76	77	78	78	78	
	99th	117	118	120	122	124	125	126	82	82	83	84	85	86	86	86	
8	50th	94	95	97	99	100	102	102	56	57	58	59	60	60	61	61	
	90th	107	109	110	112	114	115	116	71	72	72	73	74	75	76	76	
	95th	111	112	114	116	118	119	120	75	76	77	78	79	79	80	80	
	99th	119	120	122	123	125	127	127	83	84	85	86	87	87	88	88	
9	50th	95	96	98	100	102	103	104	57	58	59	60	61	61	62	62	
	90th	109	110	112	114	115	117	118	72	73	74	75	76	76	77	77	
	95th	113	114	116	118	119	121	121	76	77	78	79	80	81	81	81	
	99th	120	121	123	125	127	128	129	84	85	86	87	88	88	89	89	
10	50th	97	98	100	102	103	105	106	58	59	60	61	61	62	63	63	

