	90th	111	112	114	115	117	119	119	73	73	74	75	76	77	78	78	
	95th	115	116	117	119	121	122	123	77	78	79	80	81	81	82	82	
	99th	122	123	125	127	128	130	130	85	86	86	88	88	89	90	90	

Blood Pressure Levels for Boys by Age and Height Percentile (Continued)

Age (Year)	BP Percentile ↓	Systolic BP (mmHg)							Diastolic BP (mmHg)						
		← Percentile of Height →							← Percentile of Height →						
		5th	10th	25th	50th	75th	90th	95th	5th	10th	25th	50th	75th	90th	95th
11	50th	99	100	102	104	105	107	107	59	59	60	61	62	63	63
	90th	113	114	115	117	119	120	121	74	74	75	76	77	78	78
	95th	117	118	119	121	123	124	125	78	78	79	80	81	82	82
	99th	124	125	127	129	130	132	132	86	86	87	88	89	90	90
12	50th	101	102	104	106	108	109	110	59	60	61	62	63	63	64
	90th	115	116	118	120	121	123	123	74	75	75	76	77	78	79
	95th	119	120	122	123	125	127	127	78	79	80	81	82	82	83
	99th	126	127	129	131	133	134	135	86	87	88	89	90	90	91
13	50th	104	105	106	108	110	111	112	60	60	61	62	63	64	64
	90th	117	118	120	122	124	125	126	75	75	76	77	78	79	79
	95th	121	122	124	126	128	129	130	79	79	80	81	82	83	83
	99th	128	130	131	133	135	136	137	87	87	88	89	90	91	91
14	50th	106	107	109	111	113	114	115	60	61	62	63	64	65	65
	90th	120	121	123	125	126	128	128	75	76	77	78	79	79	80
	95th	124	125	127	128	130	132	132	80	80	81	82	83	84	84
	99th	131	132	134	136	138	139	140	87	88	89	90	91	92	92
15	50th	109	110	112	113	115	117	117	61	62	63	64	65	66	66
	90th	122	124	125	127	129	130	131	76	77	78	79	80	80	81
	95th	126	127	129	131	133	134	135	81	81	82	83	84	85	85
	99th	134	135	136	138	140	142	142	88	89	90	91	92	93	93
16	50th	111	112	114	116	118	119	120	63	63	64	65	66	67	67
	90th	125	126	128	130	131	133	134	78	78	79	80	81	82	82
	95th	129	130	132	134	135	137	137	82	83	83	84	85	86	87
	99th	136	137	139	141	143	144	145	90	90	91	92	93	94	94
17	50th	114	115	116	118	120	121	122	65	66	66	67	68	69	70
	90th	127	128	130	132	134	135	136	80	80	81	82	83	84	84
	95th	131	132	134	136	138	139	140	84	85	86	87	87	88	89
	99th	139	140	141	143	145	146	147	92	93	93	94	95	96	97

BP, blood pressure

\* The 90th percentile is 1.28 SD, 95th percentile is 1.645 SD, and the 99th percentile is 2.326 SD over the mean.

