Appendix 2.5 Blood Pressure Levels for Girls by Age and Height Percentile

Blood Pressure Levels for Girls by Age and Height Percentile

Age (Year)	BP Percentile ↓	Systolic BP (mmHg)								Diastolic BP (mmHg)					
		← Percentile of Height →								← Percentile of Height →					
		5th	10th	25th	50th	75th	90th	95th	5th	10th	25th	50th	75th	90th	95th
1	50th	83	84	85	86	88	89	90	38	39	39	40	41	41	42
	90th	97	97	98	100	101	102	103	52	53	53	54	55	55	56
	95th	100	101	102	104	105	106	107	56	57	57	58	59	59	60
	99th	108	108	109	111	112	113	114	64	64	65	65	66	67	67
2	50th	85	85	87	88	89	91	91	43	44	44	45	46	46	47
	90th	98	99	100	101	103	104	105	57	58	58	59	60	61	61
	95th	102	103	104	105	107	108	109	61	62	62	63	64	65	65
	99th	109	110	111	112	114	115	116	69	69	70	70	71	72	72
3	50th	86	87	88	89	91	92	93	47	48	48	49	50	50	51
	90th	100	100	102	103	104	106	106	61	62	62	63	64	64	65
	95th	104	104	105	107	108	109	110	65	66	66	67	68	68	69
	99th	111	111	113	114	115	116	117	73	73	74	74	75	76	76
4	50th	88	88	90	91	92	94	94	50	50	51	52	52	53	54
	90th	101	102	103	104	106	107	108	64	64	65	66	67	67	68
	95th	105	106	107	108	110	111	112	68	68	69	70	71	71	72
	99th	112	113	114	115	117	118	119	76	76	76	77	78	79	79
5	50th	89	90	91	93	94	96	96	52	53	53	54	55	55	56
	90th	103	103	105	106	107	109	109	66	67	67	68	69	69	70
	95th	107	107	108	110	111	112	113	70	71	71	72	73	73	74
	99th	114	114	116	117	118	120	120	78	78	79	79	80	81	81
6	50th	91	92	93	94	96	97	98	54	54	55	56	56	57	58
	90th	104	105	106	108	109	110	111	68	68	69	70	70	71	72
	95th	108	109	110	111	113	114	115	72	72	73	74	74	75	76
	99th	115	116	117	119	120	121	122	80	80	80	81	82	83	83
7	50th	93	93	95	96	97	99	99	55	56	56	57	58	58	59
	90th	106	107	108	109	111	112	113	69	70	70	71	72	72	73
	95th	110	111	112	113	115	116	116	73	74	74	75	76	76	77
	99th	117	118	119	120	122	123	124	81	81	82	82	83	84	84
8	50th	95	95	96	98	99	100	101	57	57	57	58	59	60	60
	90th	108	109	110	111	113	114	114	71	71	71	72	73	74	74
	95th	112	112	114	115	116	118	118	75	75	75	76	77	78	78
	99th	119	120	121	122	123	125	125	82	82	83	83	84	85	86
9	50th	96	97	98	100	101	102	103	58	58	58	59	60	61	61
	90th	110	110	112	113	114	116	116	72	72	72	73	74	75	75
	95th	114	114	115	117	118	119	120	76	76	76	77	78	79	79
	99th	121	121	123	124	125	127	127	83	83	84	84	85	86	87
10	50th	98	99	100	102	103	104	105	59	59	59	60	61	62	62
	90th	112	112	114	115	116	118	118	73	73	73	74	75	76	76
	95th	116	116	117	119	120	121	122	77	77	77	78	79	80	80
	99th	123	123	125	126	127	129	129	84	84	85	86	86	87	88

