Vital sign values will be considered PCI if they meet the criteria listed in [Table 6](#) for Age 4-5 or if they meet the criteria in [Table 7](#) for Age 6-12. The number and percentage of subjects with PCI post-baseline values will be summarized. The percentages will be calculated relative to the number of subjects with baseline and at least 1 post-baseline assessment. The numerator is the total number of subjects with at least 1 PCI post-baseline vital sign value. A supportive listing of subjects with post-baseline PCI values will be provided including the treatment group of the antecedent studies, subject number, site, baseline, and post-baseline PCI values. A listing of all AEs for subjects with post-baseline PCI vital sign values will also be provided.

Table 6 Criteria for Potentially Clinically Significant Vital Sign Findings in Subjects Aged 4-5 Years

Vital Sign Parameter	Flag	Criteria ^a	
		Observed Value	Change from Baseline
Sitting Systolic blood pressure (mmHg)	High	≥120	Increase of >10
	Low	<75	Decrease of >10
Sitting Diastolic blood pressure (mmHg)	High	≥85	Increase of >10
	Low	<40	Decrease of >10
Pulse rate (beats per minute)	High	≥130	Increase of >15
	Low	≤55	Decrease of >15
Weight (kg)	High	-	Increase of ≥7%
	Low	-	Decrease of ≥7%
Temperature (deg. C)	High	>39	-
	Low	<35	-
BMI (kg/m ²)	High	>95th percentile for age and sex	-
	Low	<5th percentile for age and sex	-

^a A post-baseline value is considered a PCI finding if its meets either the criteria for observed value or the criteria for the change from baseline.

Age is calculated from the informed consent date from antecedent studies for Group A and from the informed consent date from SHP465-308 for Group B.

Table 7 Criteria for Potentially Clinically Significant Vital Sign Findings for Subjects Aged 6-12 Years

Vital Sign Parameter	PCI Criteria
Weight Loss (kg)	≥7% of weight (determined at baseline)
Systolic BP (mmHg), seated, 6 – 12 years~	>120* >120* on 2 or more consecutive visits >10 increase from baseline >10 increase from baseline on 2 or more consecutive visits >120* and increase >10 from baseline >120* and increase >10 from baseline on 2 or more consecutive visits
Diastolic BP (mmHg), seated, 6 – 12 years~	>80* >80* on 2 or more consecutive visits >10 increase from baseline >10 increase from baseline on 2 or more consecutive visits

Table 7 Criteria for Potentially Clinically Significant Vital Sign Findings for Subjects Aged 6-12 Years

Vital Sign Parameter	PCI Criteria

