	>80* and increase >10 from baseline >80* and increase >10 from baseline on 2 or more consecutive visits
Pulse (beats/minute)	<=50* <=50* and decrease >15 from baseline >=100* >=100* on 2 or more consecutive visits >=100* and increase >15 from baseline >=100* and increase >15 from baseline on 2 or more consecutive visits
Temperature (tympanic)	>38.0°C (100.4°F)
Temperature (oral)	>37.5°C (99.5°F)
Respiratory Rate (breaths per minute)	<10 or >24

~Given the pharmacological effect of the drugs used in ADHD and based on experience gained in previous ADHD trials, the focus is on rise of blood pressure only.

*The NCI has not specified a value, Shire physicians have agreed on values provided.

Age is calculated from the informed consent date from antecedent studies for Group A and from the informed consent date from SHP465-308 for Group B.

Pulse rate (beats per minute) will be considered abnormal if a value is lower than the 1st percentile or higher than the 99th percentile cut-off values listed in [Table 8](#).

Table 8 Normal Range of Pulse Rate (beats/min)

Age	1 st Percentile	99 th Percentile
	Males	
4-5 years	69	120
6-8 years	59	114
9-11 years	56	110
12 years	52	108
	Females	
4-5 years	70	132
6-8 years	61	117
9-11 years	58	113
12 years	54	110

Source: National health statistics report: Resting Pulse Rate Reference Data for Children, Adolescents, and Adults: United States, 1999–2008

<https://www.cdc.gov/nchs/data/nhsr/nhsr041.pdf>

The number and percentage of subjects with abnormal pulse rate values for at least 1 post-baseline assessment will be tabulated by treatment group of the antecedent studies, current treatment (SHP465) for each enrollment type, and overall for the lower than the 1st percentile

and higher than the 99th percentile cut-off values, respectively, for male and female separately. The denominator will be the number of subjects in the Safety Set (per gender) with at least 1 post-baseline pulse measurement. The numerator is the total number of subjects with at least 1 abnormal pulse record. A supportive listing of subjects with abnormal pulse rate values will be provided.

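### SAP Table 6 puts the low diastolic limit for ages 4-5 (<40 mmHg) inside the ordinary range of the protocol's own norms, so the Low PCI percentage cannot be read as a hypotension signal

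*SAP*

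**What the plan says.** SAP section 11.3 defines PCI vital-sign findings in Table 6 for ages 4-5 and Table 7 for ages 6-12. In Table 6 the low diastolic entry is "Low <40 Decrease of >10", and the high entry in the same block is a value of 85 or more, or an increase above 10. Footnote a makes either route sufficient: "A post-baseline value is considered a PCI finding if its meets either the criteria for observed value or the criteria for the change from baseline". A subject enters the numerator after one qualifying post-baseline value. The value used is the mean of the three readings at the visit.

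Table 7 has no low blood pressure criterion, neither a value nor a fall. Its footnote to the blood pressure rows says "the focus is on rise of blood pressure only". For rises it gives separate rows for the value, the change, both together, and each of these on two or more consecutive visits.

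The protocol's norms are in Appendices 2.3 (boys) and 2.5 (girls). The table note gives the scale: "The 90th percentile is 1.28 SD, 95th percentile is 1.645 SD, and the 99th percentile is 2.326 SD over the mean". The SAP gives no source or rationale for the limit of 40.

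**The concern.** A PCI limit should pick out values that are unusual for the child's age. Medians of 47-56 mmHg leave little room above 40, so many healthy children would be flagged at an ordinary visit. The SAP's norm-based limits elsewhere cut off small tails: BMI below the 5th or above the 95th percentile (Table 6), pulse below the 1st or above the 99th (Table 8), blood pressure above the 95th (Table 9).

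Blood pressure is part of the primary safety objective, and at least 40 children aged 4-5 are planned. A large Low percentage in this group could be taken for a safety finding. Every child with a PCI vital sign also enters the supportive listing and the linked listing of all adverse events.

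There is a comparability problem as well. SAP section 2.1 says study 112 enrolled ages 4-5 and study 309 ages 6-12. In the antecedent-study columns, low blood pressure findings can occur under 112 but are not defined under 309, whatever the drug does.

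**Working it through.** The plan states no expected flag rate, so there is none to reproduce. The check uses the protocol's norms.

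**Inputs.** 50th-percentile diastolic pressure over the seven height columns: boys 4, 47-52 ("4 50th 88 89 91 93 95 96 97 47 48 49 50 51 51 52 52", diastolic values last; the final value is printed twice); boys 5, 50-55; girls 4, 50-54 ("4 50th 88 88 90 91 92 94 94 50 50 51 52 52 53 54"); girls 5, 52-56. The 99th percentile for boys 4 is 74-79 ("99th 113 114 116 118 120 121 122 74 75 76 77 78 78 79 79").

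**Formulas.** SD = (99th - 50th)/2.326; z = (40 - 50th)/SD; P(<40) = Phi(z). SDs from the 90th and 95th percentiles give the same results within rounding.

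| Cell | Mean | SD | z | P(<40) per visit |
|---|---|---|---|---|
| Boys 4, median height | 50 | (77-50)/2.326 = 11.6 | -0.86 | 19.4% |
| Boys 5, median height | 53 | (80-53)/2.326 = 11.6 | -1.12 | 13.1% |
| Girls 4, median height | 52 | (77-52)/2.326 = 10.7 | -1.12 | 13.2% |
| Girls 5, median height | 54 | (79-54)/2.326 = 10.7 | -1.30 | 9.6% |
| Boys 4, 5th height percentile (highest rate) | 47 | (74-47)/2.326 = 11.6 | -0.60 | 27.3% |
| Girls 5, 95th height percentile (lowest rate) | 56 | (81-56)/2.326 = 10.7 | -1.49 | 6.8% |

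Over all 28 age, sex and height cells the unweighted mean is 14.7%.

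**Sensitivity of the per-visit rate.**
- Without the 5th height-percentile column (Protocol 4.2, criterion 7, excludes height at or below it), the maximum is about 24.5%.
- With the rise in Protocol 1.2 added to the mean: 5-22% at +2 mmHg (mean 11%), 3-17% at +4 mmHg (mean 8%).
- If the norms are single readings (the documents do not say), averaging three readings multiplies the SD by sqrt((1+2r)/3). For an assumed within-visit correlation r of 0.5 the range is 3-23%; for 0.9 it is 6-27%.

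**Comparison.** The high limit of 85 lies 2.6-3.3 SD above the mean and flags 0.05-0.5% per visit. The low systolic limit (<75) lies 1.2-2.1 SD below its mean and flags 2-11%.

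**Ever flagged.** Simulation at median height for the four age-sex groups: one baseline and 14 post-baseline visits, normal values with the SDs above, assumed between-visit correlation 0.4, 0.6 or 0.8. Ranges run over groups and correlations.

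| Diastolic rule, ages 4-5 | No drug effect | +3 mmHg |
|---|---|---|
| Value <40 | 28-73% | 19-60% |
| Decrease >10 | 37-70% | 19-59% |
| Either (Table 6 as written) | 53-89% | 33-80% |
| Both at the same visit, at least once | 12-54% | 5-39% |
| Both on 2 or more consecutive visits | 2-15% | 0.5-8% |

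With 7 visits instead of 14, the <40 row falls to 23-59% and 15-46%.

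**The case against.** The strongest reply is that the observed-value limit is not the main source of flags. That is correct. The change criterion alone flags as many children, and in the simulation <40 adds only about 12-25 percentage points of children not already flagged by a fall. The high diastolic row (85 or more, or a rise above 10) is just as busy: about 37-70% ever flagged with no drug effect and 59-80% with a 3 mmHg rise. A reader might infer that <40 dominates the PCI table, or that deleting it cures the problem. Neither follows, because deletion would leave 19-70% flagged by the fall alone.

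A reader might also infer that the SAP itself treats low blood pressure as irrelevant. It does not. The footnote belongs to the rows for 6-12 years and rests on earlier ADHD trials. Protocol 1.2 puts the pediatric studies at ages 6 to 17, so looking in both directions at ages 4-5 is a defensible choice.

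Three further points stand. The tables print nothing below the 50th percentile, so the lower tail is an extrapolation. The 27% figure is one cell at the edge of an excluded range and assumes no drug effect. Rises in blood pressure are also covered by the by-visit summaries and Table 9, so their assessment does not depend on this row. The SAP records early termination, so many children may have fewer than 14 visits.

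None of this moves 40 mmHg close to the 1-5% tails used elsewhere at typical heights.

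**Conclusion.** The point holds in this form. Against the protocol's norms, 40 mmHg lies 0.6-1.5 SD below the diastolic mean at ages 4-5. About 15% of reference children fall below it at a visit (7-27% over all cells, 7-25% without the 5th height percentile, about 3-22% with the stated drug rise). This assumes that the normal model in the table note extends downward; averaging three readings may lower the rates somewhat.

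Both parts of the Low criterion mostly capture ordinary variation. Under the visit and correlation assumptions above, the either-or rule flags 33-89% of children at least once, so the Low PCI percentage at ages 4-5 is not interpretable as hypotension. The 112 and 309 columns cannot be compared for low findings. The documents do not support saying that the limit will produce a false hypotension conclusion: the flag means only potentially important, and the listing shows baseline and flagged values. The fault is one of reporting and does not touch the discontinuation criteria in Protocol 4.3.1. It should be corrected before the PCI tables are produced.

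**What to change.** 1. Reconcile the low diastolic and systolic limits in Table 6 with Appendices 2.3 and 2.5, or state their source and rationale. Any new numeric limit is for the sponsor's clinicians.
2. In the PCI summary for ages 4-5, replace the single Low count for blood pressure with the structure Table 7 uses for rises: observed value, change from baseline, both together, and both on two or more consecutive visits, as separate rows.
3. State that interpretation rests on the joint rows, chiefly the consecutive-visit one. That row flags about 0.5-15% in the simulation; the joint criterion at a single visit still flags 5-54%.
4. Do not simply delete the observed-value limit. Keep every value in the listings.
5. Footnote the antecedent-study columns: low blood pressure PCI criteria apply to ages 4-5 only.

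The cost is a few more table rows and the matching program. Isolated low readings carry less weight in the summary, but they stay visible in the value row and the listings.

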**Methodology:**

This study is a Phase 3 long-term, open-label, multicenter, safety and tolerability study in children (aged 4-12 years, inclusive, at the time of consent was obtained in the antecedent study [SHP465-112 or SHP465-309] or at the time of consent into this study if directly enrolled) with ADHD.

Subjects enrolled in this study will be divided into 2 groups based on participation in antecedent studies as follows:

- Subjects in Group A are those who have been rolled-over from antecedent studies (SHP465-112 or SHP465-309). These subjects do not need additional screening and washout procedures.
- Subjects in Group B will be newly enrolled subjects who will be required to undergo full screening and washout before enrollment.

Subjects in Group A will participate in the following 2 study periods: (1) treatment period and (2) safety follow-up. Subjects in Group B will participate in the following 3 study periods: (1) screening and washout, (2) treatment period, and (3) safety follow-up.

For subjects in Group A, the last visit of the antecedent study, SHP465-112 or SHP465-309, will serve as the baseline visit (Visit 2) for this study. For subjects in Group B, a screening visit will precede a washout period.

Subjects aged 4-12 years will receive SHP465 at a fixed dose of 6.25 mg.

Subjects in both groups will be treated and evaluated for 12 months, and visit the site up to 15 times for subjects in Group A and up to 16 times for subjects in Group B.

The investigator or designee must obtain written informed consent from the subject's parent/LAR and documentation of assent (if applicable) by the subject before any protocol-related procedure is performed. Procedures performed at each visit for all subjects are defined in the Study Schedules: [Table 1](#) (Group A) and [Table 2](#) (Group B).

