### **2.2 Study Objectives**

#### **2.2.1 Primary Objective**

The primary objective of this study is to evaluate the long-term safety and tolerability of SHP465 at 6.25 mg administered as a daily morning dose in children aged 4-12 years (inclusive at the time of consent) diagnosed with ADHD.

The evaluation of safety and tolerability will be based on the occurrence of treatment-emergent adverse events (TEAEs), evaluation of vital signs (systolic and diastolic blood pressure and pulse), weight, height, body mass index (BMI); clinical laboratory and electrocardiogram (ECG) results; sleep assessment (Post Sleep Questionnaire [PSQ], and Children's Sleep Habits Questionnaire [CSHQ]); and responses to the Columbia-Suicide Severity Rating Scale (C-SSRS).

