11. SAFETY ANALYSES

Safety data will be analyzed for the Safety Set by treatment group of the antecedent studies, current treatment (SHP465) for each enrollment type, and overall. Safety endpoints include the occurrence of TEAEs, vital signs (systolic and diastolic blood pressure, and pulse), height, weight, body mass index (BMI); clinical laboratory and ECG results, C-SSRS, and sleep questionnaires (PSQ and CSHQ). For each safety endpoint, the last value collected before the first dose of investigational product in this study will be used as baseline for all analyses of that safety endpoint. Except for adverse event data, only post-baseline assessments from Visit 2 (Week 0) up to Visit 16 (Month 12) that were collected on or 2 days after the last dose of investigational product will be analyzed. A Final on-Treatment Assessment (FoTA) will be defined as the last valid assessment obtained after Baseline and whilst on investigational product (on or before 2 days after the last dose date).

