11.3 Vital Signs (Including Height and Weight)

The averaged values of the 3 measurements collected for blood pressure and pulse at each visit will be used for all summaries and determination of PCIs. Summaries for vital signs will be presented by treatment group of the antecedent studies, current treatment (SHP465) for each enrollment type, and overall.

Descriptive statistics for vital signs (sitting systolic and diastolic blood pressure, pulse and weight) and their changes from baseline at each post-baseline visit and FoTA will be presented in a summary table. These summaries will also include BMI. BMI will be automatically

calculated using the height and weight collected at each visit. In the case of multiple assessments at post-baseline visits, the first readable value at the visit will be used in the summary tables.

Additionally, figures with the mean change from baseline \pm SD of the vital signs values (sitting systolic and diastolic blood pressure, and pulse) will be presented by visit for each treatment group of the antecedent studies and current treatment (SHP465) for each enrollment type.

Height, weight and BMI will also be converted to percentile values based on the subject's age and sex at each visit and summarized categorically (<5th, 5th to <95th, and \geq 95th) at each visit and at the FoTA. Post-baseline shifts in height, weight and BMI percentile category (<5th, 5th to <95th, and \geq 95th) from baseline will be summarized at each visit and at the FoTA. In addition, z-scores for weight and BMI will be based on the subject's age at each visit and will be summarized categorically (<-2, \geq -2 to <-1, \geq -1 to <1, \geq 1 to <2, and \geq 2) at each visit and at the FoTA. Percentiles and z-scores will be derived using the CDC growth charts ([Kuczmarski et al. 2002](#)). A SAS program for the 2000 CDC Growth Charts will be used to derive the percentiles and z-scores (www.cdc.gov/nccdphp/dnpao/growthcharts/resources/sas.htm).

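### The weight PCI rows in SAP 11.3 cannot be read as growth findings: at ages 4-5 the increase row is mixed with normal growth and follow-up time, and the loss rows see only actual weight loss

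*SAP*

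**What the plan says.** Protocol 2.2.1 bases the primary safety evaluation on, among other measures, "weight, height, body mass index (BMI); clinical laboratory and electrocardiogram (ECG) results". Planned follow-up is long: "Subjects in both groups will be treated and evaluated for 12 months" (Protocol synopsis, Methodology). Protocol 7.2.3.5 has weight taken at every site visit.

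SAP 11.3 sets the weight PCI criteria by age group:

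- **Table 6, ages 4-5:** high if "Increase of ≥7" percent, low if "Decrease of ≥7" percent, both as change from baseline.
- **Table 7, ages 6-12:** loss only, "≥7% of weight (determined at baseline"). There is no increase row.

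SAP 11 fixes the reference point for safety endpoints: "the last value collected before the first dose of investigational product in this study will be used as baseline". One qualifying value is enough to count a child: "The numerator is the total number of subjects with at least 1 PCI post-baseline vital sign value". Neither table adjusts the weight criterion for age or time on study.

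The same section also plans growth-referenced summaries from the CDC charts:

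- height, weight and BMI percentile categories (below 5th, 5th to below 95th, 95th and above), with shifts from baseline, at each visit and at the final on-treatment assessment (FoTA);
- z-scores, described as "z-scores for weight and BMI will be based on the subject's age at each visit and will be summarized categorically", with cuts at -2, -1, 1 and 2.

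Table 6 also has a BMI PCI below the 5th percentile for age and sex. Table 7 has no BMI row. Continuous change from baseline is planned for weight and BMI in raw units, not for z-scores.

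**The concern.** Children are expected to gain weight over a year. A fixed percentage of starting weight, counted at any visit, then behaves badly in both directions.

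The increase row at ages 4-5 fills up as normally growing children are followed for longer. Two columns with the same growth but different exposure will show different counts, so a difference between columns says little about the drug.

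The loss row answers a narrower question than the one of interest. Protocol 1.2 lists decreased appetite and decreased weight among the known effects, so slowed gain is a plausible harm. Slowed gain is not loss and leaves no trace in this row.

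Every child receives SHP465 and there is no concurrent control, so a growth reference is the natural benchmark for weight. Elsewhere in SAP 11.3, pulse is judged against age and sex norms (Table 8) and blood pressure against age, sex and height norms (Table 9). The weight PCI has no such reference.

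**Working it through.** The plan gives no computed figure for this rule, so there is none to reproduce. The 7% is a set threshold, and the sample size is stated not to rest on statistical considerations.

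**Inputs from the documents.** Threshold 7%; fixed baseline; any one post-baseline value counts; 14 scheduled post-baseline visits (days 7, 14, then every 30 days to 360); weight at or below the 5th percentile is exclusionary (Protocol 4.2, criterion 8).

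**Assumptions, not in the documents.** Mean normal gain g of 6-15% of body weight a year; between-child SD of annual gain 3-5 percentage points; weighing error 1%; coefficient of variation (CV) of weight for age 12-18%.

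**1. When an average child crosses +7%.** Months = 12 × ln(1.07) / ln(1+g). For g = 10%: 12 × 0.0677 / 0.0953 = 8.5 months. The results for all g are in the table.

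**2. Share of normally growing children ever flagged high.** 100,000 children were simulated with linear gain, the 14 visits and the assumptions above. Ranges cover SD 3 and 5 points.

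| Assumed g | Months to +7% | Flagged by month 6 | Flagged by month 12 |
|---|---|---|---|
| 6% | 13.9 | 4-10% | 44-46% |
| 8% | 10.5 | 9-17% | 61-68% |
| 10% | 8.5 | 20-26% | 75-86% |
| 12% | 7.2 | 35-39% | 85-95% |
| 15% | 5.8 | 60-63% | 95-99.5% |

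At g = 10%, going from 6 to 12 months of follow-up raises the count from 20-26% to 75-86% with no change in growth.

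**3. What the loss row can see.** A child with zero gain has a 0% change; this needs no growth figure. In simulation with 1% weighing error, 0.0% of such children reached -7%. To meet the rule at month 12, a child must be below expected weight by 1 - 0.93/(1+g): 12.3% at g = 6%, 13.9% at 8%, 15.5% at 10%, 17.0% at 12% and 19.1% at 15%.

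**4. What the other planned outputs would see after a year of zero gain.** The fall in weight z-score is about d = ln(1+g)/CV. For g = 8% and CV 15%: 0.077/0.15 = 0.51. Over g = 6-15% and CV 12-18%, d runs from 0.32 to 1.16.

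- *Shift below the 5th percentile*, with baseline above the 5th: [Φ(-1.645+d) - 0.05]/0.95. For d = 0.51 this is 8.3%. The full range is 4.5-28%.
- *Change of z-score band*: 18-71% of children. The z-score table is by visit and not a shift table, so this would appear only as a change in the group distribution.
- *Band width*: the 5th to below 95th category spans 1.645 + 1.645 = 3.29 SD. A child starting at the median would have to fall 1.645 SD to leave it. The largest fall above is 1.16.

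**The case against.** The strongest reply is that the weight PCI rows are not the SAP's growth analysis and should not be judged as if they were. Much of this stands.

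- SAP 11.3 plans age- and sex-referenced percentile shifts from baseline. Because low weight at entry is exclusionary, a shift below the 5th percentile is a new on-study event.
- At ages 4-5, a child who grows taller without gaining weight can meet the BMI below 5th percentile PCI.
- SAP 11.1.1 gives weight decrease and decreased appetite their own adverse event analyses, including onset, duration, severity and month.
- The 7% loss cut matches the figure in Protocol 7.2.3.12, and Table 7 labels its row as weight loss. It does what its label says. Likewise, a high-weight flag that becomes rarer when gain slows is working as labelled.
- PCI tables are descriptive screens with supporting listings; no formal tests are planned.

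A reader might infer that the SAP as a whole misses growth suppression, or that a child who stops gaining is never picked up. The outputs above rule that out; the limitation belongs to the weight PCI rows.

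What the reply does not remove is the coarseness shown in step 4 and the absence of any change-from-baseline summary for z-scores. It also leaves the Table 6 increase row without a usable interpretation. Early termination (SAP 1) lowers the expected number of high flags, but unequal follow-up makes the count depend more on time observed.

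**Conclusion.** The point holds for the weight PCI rows. That the loss rule cannot register slowed or absent gain follows from the rule alone, at all ages. That the increase row is confounded with growth and follow-up applies only to ages 4-5, and its size depends on assumptions: 44% to over 99% of normally growing children flagged by month 12, and 4-63% by month 6, for assumed gains of 6-15% a year.

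A reader might conclude that most completers aged 4-5 would be flagged. The documents do not establish this. They give no growth rate, and at 6% a year the average child would need 13.9 months and fewer than half would be flagged by month 12. They also do not give the exposure distribution after the termination decision of 14 Dec 2018, so the number of children with 12 months of data is unknown.

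The gap is therefore one of reporting: a weight variable named in the primary safety objective has no finely graded, growth-adjusted, within-child summary. It is worth closing because the z-scores are already to be derived.

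**What to change.** In SAP 11.3:

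1. Add a continuous summary of change from baseline in the CDC weight and BMI z-scores, by visit and at FoTA, for both age groups.
2. Delete the Table 6 weight-increase row, or replace it with an age- and sex-referenced criterion.
3. Keep the 7% loss count in Tables 6 and 7, labelled as weight loss only.

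If a z-score cut-off is wanted for a new PCI row, the sponsor should set and justify it; the documents offer no basis for a particular value.

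The cost is some SAP wording and a few table rows. No new data are needed, since the CDC program named in SAP 11.3 already yields the z-scores. The downside is less direct comparability with PCI tables from other studies that use the same 7% rule.
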